Objective: This study aims to 1) investigate the impact of ACP ageing on CRM skills and 2) assess whether ageing influences CRM learning from high-fidelity simulation. We hypothesize that (i) in ACP, baseline CRM performance will decline with increasing age and that (ii) age will negatively impact CRM learning after simulation-based education.

Methods: This will be a prospective multi-center trial. Seventy participants will individually manage a simulated crisis (pre-test) to assess the baseline effect of age on CRM skills. After an instructor-led debriefing, another simulated crisis (immediate post-test) and a third simulated crisis (retention post-test) three months later. All scenarios will be video-recorded and rated by blinded raters using validated tools. Regression analysis will be performed to determine the effect of ACP's age on baseline performance and learning.

Significance: This study will be the first prospective trial to delineate the effect of ageing on CRM performance and learning in a simulated setting. The results will help shape national policy regarding practice assessment and help tailor continuing medical education.

Background

Physician demographics

The proportion of older acute care physicians (ACP) has been steadily increasing.¹ Within Canada, approximately 32% - 39% of anesthesiologists are over the age of 55. A recent survey of members of the American Society of Anesthesiologists in 2013 revealed that a greater percentage of members are older (>55) in 2013 compared to 2007. These numbers are similar for emergency and critical care physicians where the proportion of the workforce over 55 is also 33-40%.² This shift in the demographics may be explained by various factors. It can partially be attributed to the recent economic crisis leading to delayed retirement. Also, in the early 1990s, there was a reduction of residency positions, likely explaining the smaller population of middle aged ACP and hence, increasing demand for the older population to meet the needs of the healthcare system.^{3,4} Recent studies have also reported an overall shortage of healthcare providers of all ages with conditions varying by region. This is another reason for a greater number of older ACP currently working, as it calls upon delayed retirement of the older physicians to meet the demands of the healthcare system secondary to this shortage.⁵⁻⁷

Consequences of Ageing

Acute care specialties such as critical care, emergency medicine and anesthesia, require for its providers to both excel at technical and non-technical skills and function at a high cognitive level in a fast paced environment that requires quick decision-making and problem solving. Ageing in itself is associated with physiological changes, which in turn can influence a physician's clinical abilities and decision-making. Stress impacts the ageing physician to a greater extent with potential consequences on performance, and the prevalence of stress, illness, fatigue, and dementia increases as one ages.^{3,8-11} Manual dexterity can also be affected with the onset of arthritis and alterations in visual acuity.^{3,12} Siu et al. looked at anesthesiologists' performance on a simulated airway emergency requiring cricothyroidotomy and found that operator age and years from residency were associated with decreased proficiency.⁵ Similarly, the time required for processing information is prolonged and decision-making can be compromised in physicians as they age.^{8,10,11,14}

Research investigating how such ageing-related physiological changes affect clinical performance and patient safety is lacking.^{12,15} It has been postulated that ageing physicians compensate through experience and pattern recognition of crises they have managed during their practice.^{13,14} However, Duclos et al. found that older surgeons had an increased rate of patient complications after thyroid surgery.¹⁶ The litigation data, over 10 years, of Anesthesiologists in British Columbia, Ontario, and Quebec, show that those older than 65 have 1.5 times the risk of being found responsible for litigation compared with those aged less than 51 and the settlement were generally larger.^{14,15} Disciplinary incidents involving physicians are likely to occur later in practice, increasing with each 10-year interval since first getting their license.^{14,15,17} Moreover, the degree of injury identified in the claims of older physicians was of greater severity.¹⁴

Crisis resource management and the ageing physician

Crisis Resource Management (CRM) skills are essential clinical skills within acute care specialties, and are vital for patient safety. In addition to technical skills (e.g. defibrillation, drug preparation, intubation), a rapid and organized approach to non-technical, cognitive skills such as decision-making, task management, situational awareness and team management are needed for successful CRM. High-fidelity full body mannequin simulation-based education is effective for learning CRM, including transfer of skills from the simulated setting to the clinical setting and improving patient outcome.^{4,18} However, there is a gap in the literature on whether physicians' age influences baseline CRM performance and also learning from simulation-based education.

Simulation and the ageing physician

Although the effectiveness of high-fidelity simulation-based education has been studied extensively in junior learner populations (students, residents, fellows), there are a limited number of studies investigating its effectiveness in teaching CRM in the ageing physician population.¹⁹ In fact, a recent systematic review looking at the role of simulation in continuing medical education in ACP supported that there is limited evidence supporting improved learning.²⁰ However, it is being recommended as a training, regulation and assessment tool for practicing physicians.^{12,21}

Simulation fidelity adds to its effectiveness. Increasing fidelity relies on three components: physical (actual OR environment), functional (how actions and consequences match the real-world) and psychological (how engaged the learners are with the simulation).²² The first two components can be manipulated by the simulation provider and equipment but the psychological component is highly dependent on the learner. Ageing physicians likely did not train with mannequin-based simulation compared to their younger counterparts and might have a preconceived bias against such technology. In fact, a survey on the barriers of simulation based education found that staff, compared to trainees, had less experience with simulators, found it less relevant for their current training, and perceived more barriers.²³ Hence, older physicians might not be fully committed to, or believe in the practice of mannequin-based simulation, thus reducing fidelity and its effectiveness.

Objectives and hypotheses:

The goals of this study are to:

- 1) Investigate whether ageing has an effect on baseline CRM skills of ACPs, (emergency, critical care, anesthesia) using simulated crisis scenarios and
- 2) Assess whether ageing influences learning from high fidelity simulation.

We hypothesize that:

1) ACP baseline simulated CRM performance will decline with increasing age,

2) Although all ACP performance will improve at the immediate post-test, increasing age will be negatively impact the retention of CRM skills 3 months following a high-fidelity simulation-based education session.

Methods

Study Design

This study is a prospective cohort multicenter study. Ethical approval will be sought from the Ottawa Health Science Network Research Ethics Board & Sunnybrook Research Ethics Board (Toronto, Canada). Written informed consent and a confidentiality agreement will be obtained from all participants. ACP from the academic affiliated sites of both universities will be recruited, with data collection being conducted locally in each city.

Recruitment and orientation

Practicing emergency, critical care and anesthesia staff with a minimum 5 years of practice post residency will be approached for participation.

The participants will take part in three 8-minute simulated crisis scenarios based on current Advance Cardiac Life Support (ACLS) guidelines for pulseless electrical activity (PEA) arrests. The scenarios will serve as pre, immediate post and retention tests. These scenarios will be identical for pediatric anesthesiologists, however the "patient" in the scenario will be of 15 years of age, rather than an adult. Although all three scenarios will ultimately result in PEA arrests, each will have a unique inciting event and these will be randomly assigned. Participants will be unaware as to which scenarios they will be asked to manage. All scenarios will be recorded. Confederates will serve as the patient's nurse and respiratory technician to be directed by the participant, but they will not provide tips or guidance in terms of how to manage the crisis.

A standardized structured orientation session will be held for all participants. During this session, the principles of simulation-based education will be discussed and the participants will be exposed to the simulation room, all equipment and simulators. Since participants will likely have various types of previous simulation experience, each participant will be familiarized with the simulator by participating in an introductory noncrisis scenario that will not require crisis resource management skills. The scenario will be an induction of general anesthesia using a rapid sequence induction (a common technique for the three acute care specialties in this study). Participants will also complete two questionnaires collecting demographic data (Appendix A), quantifying previous simulation and crisis management experience, and a life expectancy questionnaire online to calculate their "health age". The online questionnaire consists of questions that evaluate physiological and lifestyle factors contributing to one's "health age" and will calculate a person's "health age" based on responses. The participant will record their health age on the demographic questionnaire (Appendix A).

Scenarios

Each participant will then manage a PEA arrest scenario (pre-test) and then be debriefed on their CRM skills by a trained facilitator for 20 minutes. They will then manage another crisis scenario (PEA arrest once again, but with a different inciting event) as an immediate post-test. Three months after completing the instructional session, participants will return to manage a third PEA arrest scenario, which will serve as a retention post-test in additional to completing a retention questionnaire (Appendix D). The retention posttest can be completed up to 6 months following the initial pre-test. All three scenarios will be designed with the same clinical scenario that is common to all ACPs but the physical simulation environment will be set-up according to their specific specialty (i.e. ICU, OR, and ER) so that they are familiar with their unique layouts. All debrief sessions will be recorded as a quality control measure to ensure that all debriefs are conducted in a consistent manner.

Simulation Scenario Development

The core concepts pertaining to CRM skills and subsequent management of PEA arrest will be consolidated by the principal investigators and then sent out to three faculty acute care physicians (one from each specialty involved) from Universities not involved in the recruitment, who are trained ACLS instructors, for review and revisions. Once core concepts are agreed upon, the three simulation scenarios will be developed. Each scenario will then be piloted before recruitment.

Outcome measures:

As our primary outcome, we will assess the relationship of age with:

A) CRM skills, as measured by (Appendices B & C):

- a. Ottawa GRS scale total score (non-technical CRM skills)²⁴
- b. official ACLS checklist for PEA (technical CRM skills)²⁵

B) Learning* from high-fidelity simulation based education, as measured by change in performance (Appendices B & C):

1) official ACLS checklist for PEA²⁵,

2) Ottawa Global Rating Scale for CRM²⁴

* Learning defined as improvement in performance in the simulation based crisis scenarios.

Two raters blinded to the study hypotheses and the scenarios order (pre vs immediate post vs retention post-test), will evaluate the videos using the above validated tools.

Statistical Analysis and Sample Size Calculation

To test the first hypothesis, a multivariate regression analysis will be performed, with age as a predictor and outcomes A (listed above) as the dependent variables. To test the second hypothesis, a second multivariate regression analysis will be performed with age, pre-test score, post-test scores and their interactions (age x pre-test score, age x intervention, age x pre-test score x intervention, and pre-test score x intervention) as predictors, and outcomes B on the retention test (listed above) as the dependent variables.

To adequately power our study, we will need at least 10 participants per predictor variable entered into the analysis. In order to collect a meaningful sample, we will aim to recruit 10 participants per 10 year age group (<45, 45-54, 55-64, 65+), equaling 40 ACP. To account for attrition, we will aim to recruit 70 participants total across both sites.

Timeline

This study will run for 2 years:	
Ethics Submission:	Months 1-3
Content Development & Pilot Scenarios:	Months 3-4
Data Collection:	Months 5-15
Statistical Analysis:	Months 16-17
Manuscript & Dissemination of results:	Months 18-24

Dissemination Strategy

Upon completion of this study, the results will be presented to educators and clinicians in the local Departments of Anesthesia, Critical Care and Emergency Medicine for further discussion in addition to providing an opportunity for other educators to explore the creation of a continuing education curriculum within their practice groups. Initially, this will be done at a local level during medical rounds presentations and seminars at the Universities of Toronto and Ottawa. We will submit our study for publication in peer reviewed medical education journals to reach a broader audience. If possible, we will publish the manuscript as open access to increase its citations. Applications to regional and international conference presentations will also by entered. Finally, we will approach provincial and federal regulation bodies such as the Royal College of Physicians and Surgeons of Canada to 1) open discussion for further studies building on our results and 2) develop strategies for continuing education.

Implications

This study will be the first prospective trial to delineate the effect of ageing on CRM performance and learning in a simulated clinical setting. As such, the results will help shape not only national policy regarding practice assessment, and help develop continuing education for ageing physicians. The results can also serve as foundation for research in specialties other than acute care. Similarly, in the very least, whether ageing influences CRM skills or not, this study can serve as a template for investigation in non-acute care specialties as well.

References

- 1. Geographic Distribution of Physicians in Canada. Canadian Institute for Health Information, 2005
- 2. Association of American Medical Colleges. Center for Workforce Studies: 2012 Physician Specialty Data Book. 2012
- 3. Katz JD: Issues of concern for the aging anesthesiologist. Anesthesia & Analgesia 2001; 92:1487–92
- 7. Administration USHRAS: The Critical Care Workforce. 2006

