Appendix A – Demographic Questionnaire

Appendix B – Ottawa Global Rating Scale

Appendix C – ACLS (PEA) Checklist

Appendix A: Demographic Questionnaire

Age:

Sex:

- 1. Number of years practicing your specialty (Anesthesia, Critical Care, Emergency Medicine) since residency
 - 0 10 11 20 21 30 31 40 41 50 >50

2. Are you, or have you ever been an ACLS Instructor?

Yes No

3. What percentage of time have you managed ACLS crises in your practice?

0-10 % 11-20% 21-30% 31-40% 41-50% >50%

- 4. A) How many times have you experienced Full Body Mannequin Simulation (# of Scenarios):
 - 0-5 6-10 11-15 16-20 >20

B) Please indicate the type of scenarios managed (check all that apply):

ACLS Procedural Rare Cases (ie MH) Crisis Resource Management

Please go to www.projectbiglife.ca. to complete the Life Expectancy Questionnaire.

Write the reported Health Age below:

Health Age:

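### Participants work out and write down their own health age before the pre-test that is regressed on age; this ageing cue is avoidable and can be moved to after the immediate post-test

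*Combined protocol and SAP*

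**What the plan says.** Under Recruitment and orientation, the protocol describes a standardised orientation, a non-crisis introductory scenario, and paperwork: "Participants will also complete two questionnaires collecting demographic data (Appendix A), quantifying previous simulation and crisis management experience, and a life expectancy questionnaire online". The online tool returns a result to the participant, and "The participant will record their health age on the demographic questionnaire (Appendix A"). Appendix A opens with age and sex, asks about years in practice, ACLS work and earlier simulation experience, sends the participant to a website "to complete the Life Expectancy Questionnaire", and ends with "Write the reported Health Age below".

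The next section, Scenarios, begins: "Each participant will then manage a PEA arrest scenario (pre-test) and then be debriefed on their CRM skills". No step is described between the orientation and this test, and no section places the questionnaires after testing.

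Under Statistical Analysis and Sample Size Calculation, hypothesis 1 is tested by a regression "with age as a predictor and outcomes A (listed above) as the dependent variables". The learning regression uses age, the pre-test and post-test scores and their interactions to predict the retention-test outcomes. Health age is in neither model. The raters are blinded to the hypotheses and to scenario order. For participants, the only masking stated is that they do not know which scenario they will face.

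**The concern.** Age is the exposure, and pre-test performance is the outcome for hypothesis 1. Between recruitment and that outcome, the plan has each participant answer questions about their own life expectancy, read a personal health age and write it down. If this unsettles older physicians more than younger ones, part of any fitted decline with age would come from the study procedure. The protocol gives one reason to take the possibility seriously. Under Consequences of Ageing it says: "Stress impacts the ageing physician to a greater extent with potential consequences on performance".

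The analysis could not repair such an effect. Blinded raters would correctly score a performance that had itself been altered. Because everyone receives the cue, a response to it that varies with age cannot be separated from age in the regression. The sponsor intends the results to inform national policy on practice assessment, so a rival explanation that costs almost nothing to avoid is worth removing before data collection.

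**Working it through.** The plan has no figure of its own on this point, so the check covers the order of procedures, what the regression can absorb, and an illustration of size.

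**1. Order.** Recruitment and orientation contains the questionnaires and the recording of health age. Scenarios follows and says that participants then manage the pre-test. The cue precedes the outcome on the natural reading. The length of the gap is not stated, nor is the order of the forms relative to the introductory scenario.

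**2. What the regression absorbs.** Write the pre-test score as a + b·age + c(age) + error, where c(age) is the effect of the cue.
- If c is the same at every age, only the intercept moves and b is unbiased.
- If c falls with age, the fitted slope is too negative, which favours hypothesis 1.
- If c rises with age (a reassuring result for older physicians), the fitted slope is biased towards zero or upwards.

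**3. Size under an assumed pattern.** The documents give no effect size, so every input here is an assumption except the four age groups (<45, 45-54, 55-64, 65+). Assume equal groups centred at 40, 50, 60 and 69, a uniform 10-year spread within each, and decrements of 0, 0, d/2 and d in SD units of the score.
- Mean age: (40 + 50 + 60 + 69)/4 = 54.75. Deviations: -14.75, -4.75, 5.25, 14.25.
- Between-group variance: (217.56 + 22.56 + 27.56 + 203.06)/4 = 117.69. Within-group variance: 100/12 = 8.33. Total: 126.02.
- Covariance of age with the decrement: (5.25·d/2 + 14.25·d)/4 = 4.219d.
- Artificial decline: 4.219d/126.02 = 0.0335d per year, or about 0.335d per decade.

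| Assumed d in the 65+ group (SD) | Artificial decline (SD per decade) |
|---|---|
| 0 | 0 |
| 0.2 | 0.067 |
| 0.3 | 0.100 |
| 0.5 | 0.167 |

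Reversing the sign of d reverses the sign of the bias.

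**4. Sensitivity to the pattern.** A different assumption is a single drop of d for everyone aged 55 or over, with ages 35 to 75 in equal groups. The slope is then (0.25 × 20·d)/(40²/12) = 5d/133.3, or 0.375d per decade. A simulation with no true age effect, a two-sided 5% test and 20,000 runs per setting gave these rates of a falsely significant age effect:

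| d (SD) | n = 40 | n = 70 |
|---|---|---|
| 0 | 4.6% | 5.1% |
| 0.2 | 8.8% | 10.9% |
| 0.3 | 12.4% | 18.2% |
| 0.5 | 25.9% | 42.9% |

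These rates show how sensitive the test would be if such an effect existed. They are not evidence that it does.

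**5. Learning.** Appendix D repeats neither the age item nor the calculator at the retention visit. If the cue lowers only the pre-test, a later-minus-earlier change is inflated by d/2 at 55-64 and by d at 65+. Under the pattern in step 3, that adds 0.335d per decade to the age slope of the gain. Hypothesis 2 predicts poorer retention with increasing age, so this bias runs against it.

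**6. Effect of reordering on the plan.** The stated numbers are 4 × 10 = 40, raised to 70 for attrition. Health age is not a predictor in either regression, so moving it changes neither the sample size nor any named term.

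**The case against.** The strongest reply is that the documents show exposure to a cue and nothing more. No section says that reading a health age alters performance, and the sentence on stress concerns ageing physicians in general, not the effect of a questionnaire. That stands.

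The direction is also open. The tool draws on physiological and lifestyle factors, so a practising physician of 65 or over may receive a reassuring figure and a younger one an unwelcome figure. That stands too, and the size above must be read with either sign.

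A reader might infer that the cue comes immediately before the pre-test. The text does not support this: it gives no interval, does not say that orientation and pre-test fall on the same day, and leaves room for the introductory scenario in between.

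A reader might also conclude that the whole of Appendix A should move. That goes too far. Collecting baseline characteristics before testing is ordinary practice, and self-reported ACLS and simulation experience could be coloured by two scored crises and a debrief if it were asked afterwards.

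Finally, participants may know from other sources that the study is about ageing, since it recruits by age group and the consent pages are not in the review copy. Reordering would then remove only the increment due to the personal health-age result. This limits the benefit, but it is no reason to keep the item before the test.

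**Conclusion.** The point holds as a low-cost improvement in the order of procedures. As written, participants generate and record a personal ageing result before the outcome that is regressed on age, and neither rater blinding nor the planned model could remove a response to it that differs by age.

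The bias is possible, not demonstrated. A stronger reading, that the baseline age slope is biased towards hypothesis 1, is not supported, because size and direction are both absent from the documents and a uniform effect would leave the slope unbiased. Nor would the cue favour both hypotheses: an effect that lowers older physicians' pre-test scores and then fades would help hypothesis 1 and work against hypothesis 2.

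The range of 0 to 0.17 SD per decade rests wholly on an assumed decrement of 0 to 0.5 SD in the 65+ group, half that at 55-64, and equal age groups. A reassuring result would give bias of the opposite sign.

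**What to change.** Move the online life-expectancy questionnaire and the Health Age item of Appendix A to the end of the first session, after the immediate post-test. Take age (for the recruitment group), specialty (for the room set-up) and years since residency (for the five-year eligibility rule) at recruitment. The ACLS and simulation experience items may stay before the pre-test, so that performance does not colour the answers. State in Recruitment and orientation and in Scenarios where each form falls in the sequence.

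The cost is a change in the order of session-one procedures and a split of Appendix A into two parts. There are no added visits, and the sample size, outcomes and regressions are unchanged. A participant who leaves early may have to return the health-age item later. Other cues about the study's ageing topic may remain, so the change reduces the risk without necessarily removing it.

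### The retention model has no term for time since training, although the retention test may fall anywhere from about 3 to 6 months; adding months as one covariate is a minor, inexpensive improvement.

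*Combined protocol and SAP*

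**What the plan says.** Under Objectives and hypotheses, the second hypothesis concerns "retention of CRM skills 3 months following a high-fidelity simulation-based education session". The opening summary describes "a third simulated crisis (retention post-test) three months later", and the Scenarios section says "Three months after completing the instructional session, participants will return to manage a third PEA arrest scenario". The Scenarios section then widens the timing: "The retention posttest can be completed up to 6 months following the initial pre-test". No earliest date is given.

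Under Statistical Analysis and Sample Size Calculation, the retention model takes "outcomes B on the retention test (listed above) as the dependent variables". Its predictors are "age, pre-test score, post-test scores and their interactions", with the interactions given as "age x pre-test score, age x intervention, age x pre-test score x intervention, and pre-test score x intervention". That is three main effects and four interactions, seven terms in all. None involves elapsed time, and no restriction or sensitivity analysis on timing is described. The sample-size rule in the same section is "we will need at least 10 participants per predictor variable entered into the analysis".

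**The concern.** The retention score is the dependent variable for hypothesis 2, so time since training bears directly on it. The window lets some participants be tested at close to twice the hypothesised interval, and the model treats all of them as one retention test.

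Two separate things could follow.

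- **Confounding.** If older participants tend to return later (or earlier) than younger ones, and skill fades with time, the age slope picks up part of the fading.
- **Time point.** If age-related loss grows with time, the age slope describes the average delay and not 3 months, even when delay is unrelated to age.

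If neither holds, the omission costs only a little noise.

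**Working it through.** **The plan's own figures.** 10 participants x 4 age groups = 40, which reproduces. Recruitment is set at 70 for attrition, with no rate stated. The listed model has 3 + 4 = 7 terms, and 7 x 10 = 70 under the rule of 10 per predictor.

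**Assumed inputs (none is in the documents).**
- Decay: 0.1 to 0.2 outcome SD per month.
- |corr(age, delay)|: 0, 0.3 or 0.5.
- Delay: either even over 3 to 6 months (mean 4.5, SD 3/√12 = 0.866) or clustered near 3 as 3 + 3 x Beta(1,4) (mean 3.6, SD 0.490).
- Completers: 40 or 70.
- The interaction factor called *intervention* is undefined for a single cohort. It is read here as the immediate post-test score, and the simulated figures depend on that reading. Scores are centred in the simulation.

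**Step 1: spurious age slope when the true slope is zero.** Slope = correlation x SD of delay x decay.
- Zero correlation: 0.
- Smallest nonzero case: 0.3 x 0.490 x 0.1 = 0.015 SD per SD of age.
- Largest case: 0.5 x 0.866 x 0.2 = 0.087.
- The sign follows the sign of the correlation.

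**Step 2: false-positive rate in the plan's seven-term model, nominal 5%.** The rows use decay 0.2 and correlation 0.5. In the last two columns, the second figure applies when pre-test and post-test scores explain half the variance.

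| Delay | n | Without months | With months |
|---|---|---|---|
| Even | 70 | 9.0%; 12.4% | 5.1%; 5.0% |
| Clustered | 70 | 6.9%; 7.3% | not tabulated |
| Even | 40 | 7.2%; 9.1% | not tabulated |

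Repeat runs with different seeds and set-ups gave 8.9% and 13.3% for the first row. This is why the upper end is stated as about 13%, and the 40-completer worst case as about 6.5% to 9%. Over the 16 nonzero combinations of inputs the medians are 5.4% and 5.9%. In the first row, adding months moves the spurious slope from -0.087 to 0.002 (-0.084 to -0.001 with half the variance explained).

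**Step 3: time point, with no age-delay link.** Take a true 3-month age slope of -0.30 and let the loss grow in proportion to time. The slope at the mean delay is then -0.30 x 4.5/3 = -0.45 (even) or -0.30 x 3.6/3 = -0.36 (clustered). Simulation at n = 70 with months as a main effect gives -0.449 and -0.361. For even delays, a parallel run gives -0.445 without months and -0.448 with it, so the main effect leaves the slope where it was. Adding age x months, with months centred at 3, gives -0.298 (SE 0.281) and -0.301 (SE 0.224). For even delays, 0.30/0.281 = 1.07, which is about 18% to 19% power.

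**Step 4: noise if delay is unrelated to age.** (SD x decay)² runs from (0.490 x 0.1)² = 0.0024 to (0.866 x 0.2)² = 0.030, that is 0.2% to 3.0% of score variance.

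**The case against.** The strongest reply is that nothing in the documents shows delay varying with age, and without that link there is no confounding to remove. This stands: the correlations of 0.3 and 0.5 are assumptions.

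The only route tied to the plan's own figures is the Timeline, where data collection ends at month 15. If first sessions are spread evenly from 4 to 12 months, those after month 9 cannot use the full window: 3/8 = 37.5% of participants, with a correlation of about -0.42 between entry date and delay. Age would also have to relate to entry date. At an assumed 0.3 to 0.5 for that second link, |corr(age, delay)| is only 0.13 to 0.21. With the simulated standard errors of 0.145 and 0.103, the false-positive rate is then at most about 5.7% and 6.5%.

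A reader might infer from the Background that older physicians, described there as possibly less committed to mannequin simulation, will return late and so bias the result towards the hypothesis. The text does not support this. It speaks of engagement and fidelity, not of when people attend.

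A second reply is that a months covariate does not cure the mismatch with the 3-month hypothesis. This also stands, as Step 3 shows. The covariate deals with confounding only.

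A third is that the worst cases need 70 completers and evenly spread delays, whereas the plan schedules the visit at three months and recruits 70 to allow for attrition from a base of 40. This is fair, and it is why the clustered and 40-completer results are given.

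What remains is that the plan allows the interval to vary, holds the dates needed to measure it, and does not use them.

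**Conclusion.** The point holds as a minor, inexpensive improvement. It is not a demonstrated bias. The window is disclosed and is not an error in itself; the gap is that the model takes no account of it.

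Under the stated assumptions the false-positive rate for age is about 5% to 9% at 70 participants, up to about 13% if scores explain half the variance. In the worst case at 40 completers it is about 6.5% to 9%. Most combinations sit close to 5%. At zero age-delay correlation there is no confounding, and the direction is otherwise unknown.

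A reader might also infer that centring months at 3 makes the age coefficient a 3-month effect. It does so only if the age effect does not change with delay. If age-related loss grows in proportion to time, the slope stays 1.2 to 1.5 times its 3-month value (3.6/3 and 4.5/3).

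**What to change.** 1. Derive months from the instructional session to the retention test and add it, centred at 3 months, as one covariate in the retention model for both outcomes.
2. Report the interval by age group. This uses no degrees of freedom and shows directly whether delay and age are related.
3. Pre-specify one supportive, non-confirmatory analysis adding age x months. Otherwise state that the age effect refers to the observed delay of about 3 to 6 months.

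**Cost.** No new data are needed, because enforcing the 6-month limit already requires the session dates. The main model goes from seven to eight terms: 8 x 10 = 80 participants under the plan's rule against 70 recruited, or 70/8 = 8.75 per term (40/8 = 5.0 at 40 completers). The supportive model has nine terms and would imply 90.

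If delay is unrelated to age, the standard error of the age term rises by about 1% to 2%: √(62/61) = 1.008 at n = 70 and √(32/31) = 1.016 at n = 40. At a correlation of 0.5 it rises by about 11% in simulation (0.161/0.145) and 15% by formula (1/√(1 - 0.25) = 1.155). The larger cost therefore arises only where there may be bias to remove. The supportive analysis, at about 18% to 19% power for a 3-month slope of -0.30 SD at n = 70 with even delays, can describe but not confirm.
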